8. SELECTION AND ENROLLMENT OF SUBJECTS

8.1 DESCRIPTION OF THE POPULATION

Consenting MSM and TW eighteen-year old or older, who participated and received ART in the *SABES* Study; acceptable hematologic, liver, and renal function to support an approved 3-drug ART regimen.

8.1.1 Inclusion Criteria

- 1) Age \geq 18 years
- 2) MSM or TW
- 3) Able to give consent, including consent for medical procedures, blood draws, and switching antiretroviral medication if indicated
- 4) Participants with acute/recent HIV infection who have participated in *SABES*
 - a. Current *SABES* participants, receiving ART in their assigned treatment by the time this study is implemented; or
 - b. *SABES* participants who completed 48 weeks of study participation in their

assigned treatment arm and were rolled over into the ART program sponsored by the Peruvian MOH;

- c. Any participants of the Collaborative Observational Protocol who do not meet criteria for a or b above

5) Acute/Recent HIV Participants: Already on ART, without treatment interruption, either:

- a. Receiving co-formulated EFV 600 mg, FTC 200 mg, and TDF 300 mg; or
- b. Receiving co-formulated EVG 150 mg, COBI 150 mg, FTC 200 mg, and TDF 300 mg (Stribild); or
- c. Receiving a combined ART regimen sponsored by the Peruvian MOH
- d. Prior/current participation in SABES and now receiving a non-EFV or EVG regimen with 3 active drugs (3 drugs not inclusive of the boosting agents COBI or ritonavir)

6) Seronegative participants with acute HIV infection (lack of antibodies against HIV and presence of HIV-1 RNA).

7) Kidney, liver, and hematologic functions should not prohibit ongoing administration of study drugs or else another clinically-appropriate 3-drug ART regimen (3 active drugs not inclusive of boosting agents ritonavir or COBI)

8) HIV Viral load <1000 copies/ml on the last available result (either routine clinical or study result).

9) No medical or psychiatric conditions that render the person a poor study participant in the opinion of the study physician.

10) Co-enrollment with other protocols will be at the investigators discretion.

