7.1 GENERAL STUDY DESIGN

This protocol for the MERLIN study describes the extended follow-up of participants enrolled in the *SABES* study, a study of ~250 HIV+ MSM and TGW in Lima, Perú. In this study, we will enroll up to 25 individuals with acute HIV infection.

The *SABES* study: The ongoing *SABES* study combines laboratory and epidemiologic data with

modeling to investigate the hypothesis that early ART initiation and management of alcohol use disorder will prevent onward HIV transmission among MSM/TGW diagnosed with acute (FI-FII: Ab-/HIV RNA+) or recent (≤ 3 months) HIV infection (FIII-V). The SABES study population is MSM and transgender women (TGW) not using feminizing hormones (all referred to as "MSM" from here on) in Lima. This study is being conducted in 3 phases: 1) HIV screening, 2) monthly follow-up testing of HIV-uninfected participants by point-of-care EIA and NAAT testing for HIV RNA in pools of seronegative specimens (pools are run daily), and 3) enrollment of MSM with incident HIV infection into a randomized ART treatment study (Figure 1). Only participants with acute (seronegative but HIV RNA+) or recent HIV infection (EIA+ with a prior HIV-negative test within 3 months) are eligible for enrollment in the treatment phase of the SABES study. These participants are stratified by acute vs. recent infection and randomized 1:1 to Immediate arm (to receive ART immediately) or Deferred arm (to receive ART beginning at 24 weeks or when the participant meets Peruvian treatment initiation thresholds, whichever comes first) (Figure 1). We completed enrollment of 225 HIV+ participants into the SABES study by the end of March 2016. A small number (5-10) of additional participants will be enrolled in SABES; those with symptomatic acute HIV infection will receive ART immediately, in accordance with current Peruvian treatment guidelines and will therefore not be randomized to possibly delay ART. The Human Subjects section contains a discussion of risks and benefits. All SABES participants received either EFV/FTC/TDF or EVG/COBI/FTC/TDF as first line medication. Virologic suppression at 48 and 96 weeks is equivalent for both regimens when used as initial treatment [48]; however because EVG/COBI/FTC/TDF may result in more rapid viral suppression we began using EVG/COBI/FTC/TDF for new participants when it became available as a donated drug in late 2015.

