10. STUDY PROCEDURES

10.1 Visit Program

Procedures and Sample collection		Reference to Arm of ART initiation in SABES 3	ENR (Enrollment with acute infection diagnosis)	Study week +/- 28 days				ENR 3,4 (enrollment after SABES participation)	Study week (counted since enrollment into SABES study –after HIV diagnosis) +/- 8 weeks of window								Annual Visits		Bi-annual visits
				12	24	36	48		72	96	120	144	168	192	216	Every 48 weeks after wk 192 for the immediate arm (I)	Every 48 weeks after wk 216 for the deferred arm (D)		
Informed Consent	both	X						X											
Clinical Procedures ⁵	both	X	X	X	X	X	X	X	X	X	X	X	X	X	X	X	X	X	
Questionnaire (CASI)	both	X		X		X	X	X	X	X	X	X	X	X	X	X	X	X	
Pneurophsycologic test	both	X		X		X	X	X	X	X	X	X	X	X	X	X	X		
Abdominal circumference*	both							X	✓	✓	✓	X			X	X	X		
Stool	New ENR	Immediate	X		X		X		X	X	X	X	X	X	X				
	Collection in the past	both						X	X	X	X	X	X	X	X	X	X	X	
	No collection in the past	Immediate													X ¹				
		Deferred													X ¹				
Rectal biopsy and secretion (N=60)		Immediate							X		X		X						
		Deferred								X		X		X		X			
Urine	Both	X		X	X	X	X	X	X	X	X	X	X	X	X	X	X		

BLOOD																
ART safety tests (Biochemistry, liver function and hematology)	both	X		X		X	X	X	X	X	X	X	X	X	X	X
CD4/CD8	both	X				X	X	X	X	X	X	X	X	X	X	X
HIV viral load	both	X		X		X	X	X	X	X	X	X	X	X	X	X
Lipid panel**	both	X				X	X ²	√ ²	√ ²	√ ²	X			X	X	X
Glucose**	both	X		X		X	X ²	√ ²	√ ²	√ ²	X			X	X	X
PBMC	both	X		X		X	X	X	X	X	X	X	X	X	X	X
Plasma	both	X		X		X	X	X	X	X	X	X	X	X	X	X
Whole blood (RNA LATER)	both					X	X	X	X	X	X	X	X	X	X	

Procedures and sample collection	Reference to Arm of ART initiation in SABES 3	ENR (Enrollment with acute infection diagnosis)	Study +/- 28 days week				ENR 3, 4 (enrollment after SABES participation)	Study week (counted since enrollment into SABES study –after HIV diagnosis) +/- 8 weeks of window								Annual Visits		Bi-annual visits	
			12	24	36	48		72	96	120	144	168	192	216	Every 48 weeks after wk 192 for the immediate arm (I)	Every 48 weeks after wk 216 for the deferred arm (D)			
Leukapheresis (N=40)	Inmediato								X		X		X		X				
	Diferido								X		X		X		X		X		
Dried blood	ambos						X	X	X	X	X	X	X	X	X	X	X		
Syphilis tests	ambos						X	X	X	X	X	X	X	X	X	X	X		
Max volumen of blood (ml) Including leukapheresis (if applicable)	ambos	250		250		250	250	250	250	250	250	250	250	250	250	250	250	30	

✓ conditiona procedure X obligatory procedure

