10.3.1.2 New participants with acute HIV diagnosis

The new participants entering with acute HIV diagnosis will be enrolled as soon as possible after HIV diagnosis.

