10.3.2.2. New participants with acute HIV diagnosis

Participants who enroll into MERLIN immediately after acute HIV diagnosis will initiate ART treatment within 72 hours after the enrollment visit and will have follow-up visits following Peruvian clinical care guidelines.

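### Inclusion criterion 8 (viral load below 1000 copies/mL) names no enrolment route and, as written, shuts out untreated acute participants at or above that level

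*Protocol*

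**What the plan says.** Criterion 8 in Section 8.1.1 reads "HIV Viral load <1000 copies/ml on the last available result (either routine clinical or study result". It carries no group label.

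The same list covers two kinds of participant:

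- Criterion 4 concerns people from SABES or its companion observational protocol. Criterion 5 begins "Acute/Recent HIV Participants: Already on ART, without treatment interruption, either" and then lists the permitted regimens.
- Criterion 6 admits "Seronegative participants with acute HIV infection (lack of antibodies against HIV and presence of HIV-1 RNA", with no upper limit on RNA.

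No wording makes criteria 4-5 and criterion 6 alternatives. Section 8.1, which introduces the list, describes only people "who participated and received ART in the" SABES Study.

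Other sections plainly provide for the new cohort. Section 7.1 says "we will enroll up to 25 individuals with acute HIV infection". The visit table in Section 10.1 has a column headed "Enrollment with acute infection diagnosis". Section 10.3.1.2 states: "The new participants entering with acute HIV diagnosis will be enrolled as soon as possible after HIV diagnosis". Section 10.3.2.2 adds that they "will initiate ART treatment within 72 hours after the enrollment visit". The Executive Summary (Design, and Group D), Section 8.2 and Section 10.2.2 say the same in substance, and none of them sets a viral-load limit.

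**The concern.** The eligibility list appears to have been written for people already on treatment and only partly revised when Group D was added. Criterion 8 is a natural check for someone on ART. Applied to someone diagnosed days earlier and not yet treated, it works against the purpose of the cohort.

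The Executive Summary explains that Group D was opened because few immediately treated acute participants from SABES could be eligible. If criterion 8 is enforced for everyone, the new Immediate participants are limited to those with a low pre-treatment viral load. Section 6.1 compares reservoir size and time to undetectable viral load across the Immediate, Early and Deferred groups, so selecting one group on pre-treatment viral load would disturb that comparison. If criterion 8 is ignored for Group D, each enrolment at or above 1000 copies/mL is a departure from a written inclusion criterion.

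**Working it through.** No sample size, power or error rate is at issue. The check applies the criteria to a Group D candidate and counts who is affected.

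**Inputs**

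- Ceiling for Group D: 25 (Executive Summary, Sections 7.1 and 10.2.2).
- Treatment status when eligibility is judged: untreated, since ART follows the enrolment visit (Section 10.3.2.2).
- Existing Immediate group: about 20 in the in-depth set and about 35 across all SABES (Section 4.1).
- Viral-load distribution in acute infection: not given.

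**Criteria applied to a Group D candidate**

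| Criterion | Route or status named | Result |
|---|---|---|
| 4 | SABES or companion observational protocol | Not met by a newly diagnosed person |
| 5 | Acute/recent, already on ART | Not met; untreated at enrolment |
| 6 | Seronegative acute infection | Met if RNA is present |
| 8 | None | Met only if the last result is below 1000 copies/mL |

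**Reading A: every criterion must hold.** Criterion 5 fails for every Group D candidate, 25 of 25, before criterion 8 is reached. Criterion 6 would then have no purpose, so this reading shows that the list needs an explicit alternative. It is not a forecast.

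**Reading B: (4 and 5) or 6, plus the unlabelled criteria.** The sections that provide for Group D require this reading. The number barred is the number of candidates who cannot show a last result below 1000 copies/mL. That lies between 0 and 25, and nothing in the protocol narrows it.

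**Search for an exemption.** None was found in Sections 7 to 10. None of the three amendment letters changes Section 8.1 or 8.1.1.

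**What is at stake if Group D fills.** Its share of the enlarged Immediate group would be at most:

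- in-depth set: 25 / (20 + 25) = 25/45 = 56%;
- all SABES: 25 / (35 + 25) = 25/60 = 42%.

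**A related mismatch.** Section 10.2.2 accepts either a positive RNA test or p24 antigen, with negative antibody, as the acute diagnosis. Criterion 6 requires HIV-1 RNA, and Section 4.3 also defines acute infection by RNA. A diagnosis resting on p24 alone does not document criterion 6 and provides no viral load for criterion 8.

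**The case against.** The best reply is that the intent is obvious. Criterion 6 admits viraemic seronegative people expressly, Section 8.2 offers them enrolment, and Section 10 gives them a visit schedule and an ART start. The wording of criterion 8, with its reference to routine clinical or study results, suits people already in follow-up. Amendment Letter 1 uses the same 1000 copies/mL level for people on uninterrupted treatment. On this view criterion 8 was always meant for the SABES route. That is a fair inference, and it is why the practical consequence is modest. It remains an inference: the letter concerns follow-up, not eligibility, and where its authors wanted to tie the level to treatment they said so. Criterion 8 does not.

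A second point is that a newly diagnosed person may have no quantitative result when eligibility is judged. Section 10.3.4.9 gives no turnaround time for the enrolment sample. This is true, but it does not rescue the criterion: with no result available, a value below 1000 copies/mL cannot be shown.

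Third, the 25 of 25 under Reading A depends on a reading nobody would adopt. Agreed; it is conditional and should not be used as the size of the problem.

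Finally, p24 may simply be a referral test, with RNA confirmed afterwards. That is possible, but Section 10.2.2 presents the two tests as alternatives and mentions no confirmatory step. The mismatch is real but small.

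**Conclusion.** The concern holds. As written, criterion 8 excludes an untreated acute candidate whose last viral load is 1000 copies/mL or more, although criterion 6 and the design sections invite that candidate. This is a drafting inconsistency in the eligibility rule, not a missing analysis detail, and it should be fixed.

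It touches up to 25 planned participants. With criteria 4-5 and 6 read as alternatives, the number barred is anywhere from 0 to 25. The conclusion rests on two points in the text: Group D is untreated at enrolment, and no exemption exists. Nothing in the protocol shows that anyone was turned away. No stated sample size or power depends on the matter, since Section 14.4.1 gives only the SABES step 3 participants as the enrolment goal. Selection of the Immediate group for low viral load would arise only if criterion 8 were enforced literally. The likelier cost is inconsistent eligibility decisions and recorded deviations.

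**What to change.** - In Section 8.1.1, state which enrolment route criterion 8 applies to, so that it is reconciled with criterion 6.
- In the same list, state that criteria 4-5 and criterion 6 are alternative routes.
- In Section 8.1, add the newly diagnosed acute cohort to the population description.
- Reconcile Section 10.2.2 (RNA or p24 antigen) with criterion 6 (HIV-1 RNA present).

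The cost is a minor amendment: one scoping clause, one connecting word, one sentence and one aligned phrase. Visits, procedures and sample size do not change. The choice of viral-load level and of diagnostic test is for the sponsor.

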8.1.2 Exclusion Criteria

- 1) Chronic hepatitis B co-infection
- 2) Use of drugs that are highly dependent on CYP3A for clearance (such as rifampin) which preclude administration of one of the study ART regimens or else other clinically-indicated 3-drug ART regimen
- 3) Concurrent use of aminoglycosides, IV amphotericin B, cidofovir, cisplatin, foscarnet, IV pentamidine, probenecid, adefovir or immunomodulatory agents

- 4) Any other medical or social condition that in opinion of the Investigator could affect the assessment of study objectives or put volunteers at risk.

8.2 RECRUITMENT

After the completion of the last *SABES* Study visit, participants on ART will be invited to participate in the MERLIN Study. Participants who have already completed follow-up in the *SABES* Study and were retained in clinical follow-up at IMPACTA and other clinics and received ART through a Peruvian MOH program will also be invited to participate. *SABES* participants will be eligible to transfer to the MERLIN Study (either at the end of their 48-week follow-up or when the MERLIN Study opens whichever occurs later).

To complete the initial cohort of the *SABES* 2017 study, enrollment will be offered to additional participants with acute HIV infection if those were diagnosed while seronegative, at the study site or collaboration institutions, and if they are interested in initiating antiretroviral treatment immediately in this study.

9. STUDY TREATMENT

9.1 TREATMENT REGIMENS

All participants receiving EFV-based will receive EVG/COBI/FTC/TAF.

EVG/COBI/FTC/TAF will be initiated in all participants because of the benefit of TAF compared with TDF and could have an improved metabolic risk and has demonstrable benefit on renal and bone protection

All Group C participants should be transitioned to EVG/COBI/FTC/TAF as soon as drug becomes available for distribution in the study.

All participants in groups A and B who initiated EVG/COBI/FTC/TDF should transition to EVG/COBI/FTC/TAF as soon as that drug becomes available in the study.

Participants who have initiated EVG/COBI/FTC/TAF could be switched to other antiretroviral treatment only if there is evidence of intolerance.

[figure not shown]

Figure 2.

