Participants receiving protease-inhibitor (PI)-based regimens at MERLIN enrollment will be transitioned to Genvoya after individual evaluation.

- **Group A:** This group will be comprised of persons who initiated EFV/FTC/TDF during *SABES* Step 3.

These participants will continue with EVG/COBI/FTC/TAF.

- **Group B:** This group will be comprised of persons who initiated EFV/FTC/TDF during *SABES* Step 3 and completed all 48 weeks of the protocol before MERLIN (or the Observational Study) began enrollment.

These participants were transferred to continue their in the MOH/TARGA (Peruvian Government) HIV clinics and received non-study first-line ART (EFV + lamivudine (3TC) + zidovudine (AZT), or other regimen) after completing *SABES* Step 3 and up to their enrollment in the MERLIN study.

These participants will continue treatment with EVG/COBI/FTC/TAF.

- **Group C:** This group will be comprised of persons who initiated EVG/COBI/FTC/TDF during *SABES* Step 3 or other persons currently taking a PI or INSTI-based regimens. Because INSTI-based regimens are considered preferential as described above, at MERLIN enrollment, these participants will be transferred to EVG/COBI/FTC/TAF. Persons who require to take PI-based regimens have generally had EFV intolerance/hypersensitivity or even virologic resistance. For these reasons, they cannot receive other treatments. All persons receiving PI-based regimens will also be transitioned to EVG/COBI/FTC/TAF unless a clinical contraindication exists.

- **Group D:** This group will consist of participants who were diagnosed with acute infection

and enrolled in MERLIN immediately after their diagnosis and who will initiate antiretroviral treatment immediately with EVF/COV/FTC/TAF.

Evaluations: All participants will be evaluated at regular intervals for primary and secondary outcomes.

BACKGROUND

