7.2 MANAGEMENT OF SUBJECTS WITH VIROLOGIC FAILURE OR PREMATURE DISCONTINUATION OF TREATMENT

Virologic failure is defined if there is an HIV-1 RNA of >400 copies/mL in 2 consecutive measurements after having reached an HIV-1 RNA level of <50 copies/mL in 2 consecutive measurements separated by at least 14 days.

If there is a sub-optimal virologic response, the Virologic Laboratory of the University of Washington will perform genotyping from a sample taken from before discontinuation of the treatment when the HIV-1 RNA is >500 copies/mL with the goal of determining if there has been development of resistance or not, and if yes, to help in the selection of a new antiretroviral regimen. The substituted regimen will be provided by the study while the participant is participating in the study. If the genotype does not reveal evidence of resistance and there are convincing arguments (that is to say, adherence has improved substantially or there were intercurrent illnesses that could explain the elevated viral load) the participant could continue with the original treatment plan. Any decision to continue with the regimen in the context of a suboptimal viral response must be discussed with the PI/co-PI of the study. The subsequent management of whether or not to initiate a new regimen or modify the regimen must be at the discretion of the local investigator in concordance with the standard of care. Subjects that remain in the study will be requested to complete all of the described evaluations during which time they will be provided an alternative antiretroviral treatment provided by the study.

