9.9.3 Options for Medication Substitutions Due to Intolerance/Toxicity

If intolerance or toxicity occurs, substitutions may be made to the study regimen, after discussion with the Protocol Chair, as long as the new regimen is consistent with current guidelines for potent ART. The substituted medications will be provided by the study for the duration of time that the participant remains in the study. The purpose of the study is to determine whether ART in general, not necessarily a specific regimen, affects the long-term clinical benefit for MSM and TG with different alcohol consumption levels, who acquired HIV recently. However, because in this study we are performing additional analysis comparing treatments based on EFV and EVG, those participants undergoing these medicament substitutions could be excluded from such secondary analyses.

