9.9.4 Options for Medication Substitutions for Virologic Failure

If a subject develops virologic failure on the study regimen further management based in clinical judgment should proceed at the discretion of the On-Site Principal Investigator in consultation with the Protocol Chair or Co-Chair.

Substitutions in antiretroviral regimens during the course of the study are at the discretion of the site investigator. It is the site investigator's responsibility to review all concomitant medications to ensure safety. The protocol pharmacist is available for discussion if questions arise.

The substituted medications will be provided by the study for the duration of time that the participant remains in the study.

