11.3 NEW ONSET OR WORSENING RENAL IMPAIRMENT

Renal impairment, including cases of acute renal failure and Fanconi syndrome (renal tubular injury with severe hypophosphatemia), has been reported with the use of tenofovir DF, and its co-formulations. Estimated creatinine clearance, urine glucose and urine protein should be documented in all patients prior to initiating therapy. Initiation of co-formulated EVG/COBI/FTC/TDF in patients with estimated creatinine clearance below 70 mL per minute is not recommended. Initiation of EVG/COBI/FTC/TAF in patients with estimated creatinine clearance <30 mL/min is not recommended.

Co-formulated EVG/COBI/FTC/TDF and co-formulated EVG/COBI/FTC/TAF should be avoided with concurrent or recent use of a nephrotoxic agent (e.g., high-dose or multiple non-steroidal anti-inflammatory drugs (NSAIDs)). Cases of acute renal failure after initiation of high dose or multiple NSAIDs have been reported in HIV-infected patients with risk factors for renal dysfunction who appeared stable on tenofovir DF. Some patients required hospitalization and renal replacement therapy. Alternatives to NSAIDs should be considered, if needed, in patients at risk for renal dysfunction. Persistent or worsening bone pain, pain in extremities, fractures and/or muscular pain or weakness may be manifestations of proximal renal tubulopathy and should prompt an evaluation of renal function in at-risk patients.

Routine monitoring of estimated creatinine clearance, urine glucose, and urine protein should be performed during co-formulated EVG/COBI/FTC/TDF or EVG/COBI/FTC/TAF therapy in all patients. Additionally, serum phosphorus should be measured in patients at risk for renal impairment.

Although COBI may cause modest increases in serum creatinine and modest declines in estimated creatinine clearance without affecting renal glomerular function, patients who experience a confirmed increase in serum creatinine of greater than 0.4 mg per dL from baseline should be closely monitored for renal safety.

The FTC, TAF, and TDF are primarily excreted by the kidney. Co-formulated EVG/COBI/FTC/TDF should be discontinued if estimated creatinine clearance declines below 50 mL per minute as dose interval adjustment required for emtricitabine and tenofovir DF cannot be achieved with the fixed-dose combination tablet. Co-formulated EVG/COBI/FTC/TAF should be discontinued if the creatinine clearance falls below 30 mL/min.

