13.2 PERMANENT TREATMENT DISCONTINUATION

- Drug-related toxicity (see section 9.0 Toxicity Management);
- Requirement for prohibited concomitant medications (see Section 5.3.3.);
- Clinical reasons believed life threatening by the Study Medical Director, even if not addressed in the toxicity management of the protocol;
- Suboptimal virologic response as defined in Section 4.4.;
- Subject repeatedly non adherent, to the extent that the physician believes it would not be in the subject's best interest to continue treatment;

The subjects who permanently discontinue treatment provided by the study according to the criteria described should continue a different ART regimen according to the standard of care currently in place. The study investigators will take necessary steps to ensure that the subjects continue on ART. Counseling will be provided with special emphasis on safety, and on efficacy of ART options to use in the future if the participant discontinues study ART, and does not continue with any other antiretroviral treatment.

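### Section 9.1 allows a switch off EVG/COBI/FTC/TAF only for intolerance, while Sections 7.2, 9.9.4 and 13.2 provide for a change after virologic failure or need for a prohibited drug

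*Protocol*

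**What the plan says.** **Leaving the regimen.** Section 9.1 starts EVG/COBI/FTC/TAF in all participants and closes with: "Participants who have initiated EVG/COBI/FTC/TAF could be switched to other antiretroviral treatment only if there is evidence of intolerance". Other current sections give further grounds.

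- Section 7.2 uses genotyping after a suboptimal virologic response to help choose a new regimen, and adds: "The substituted regimen will be provided by the study while the participant is participating in the study".
- Section 9.9.4, headed as options for substitution after virologic failure, says: "Substitutions in antiretroviral regimens during the course of the study are at the discretion of the site investigator".
- Section 13.2 lists suboptimal virologic response among its criteria for permanent treatment discontinuation, and also: "Requirement for prohibited concomitant medications (see Section 5.3.3". Participants who stop on these criteria are to continue on a different ART regimen. Table 1a in 9.9.2 names the drugs contraindicated with Genvoya, including rifampin.
- Section 11.3 says: "Co-formulated EVG/COBI/FTC/TAF should be discontinued if the creatinine clearance falls below 30 mL/min".
- Section 9.9.3 says: "If intolerance or toxicity occurs, substitutions may be made to the study regimen".

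**Entering the regimen from a protease inhibitor.** The Treatment Regimen part of the Executive Summary says: "Participants receiving protease-inhibitor (PI)-based regimens at MERLIN enrollment will be transitioned to Genvoya after individual evaluation". Under Group C it explains that PI users have generally had efavirenz intolerance or hypersensitivity, or even virologic resistance, and continues: "For these reasons, they cannot receive other treatments. All persons receiving PI-based regimens will also be transitioned to EVG/COBI/FTC/TAF", with an exception for a clinical contraindication. Section 9.1 says that all Group C participants should make the transition once drug is available, and mentions neither an evaluation nor an exception.

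**The concern.** The word only in 9.1 makes intolerance the sole ground for a switch. A site that follows 9.1 for a participant with virologic failure, or with a new need for a contraindicated drug, departs from 7.2, 9.9.4 or 13.2. A site that follows those sections departs from 9.1. The protocol states no order of precedence, so the conflict falls on decisions about rescue treatment and drug interactions, which bear on patient safety. Section 9.3 keeps participants on study for about 5 years, so these situations can arise long after the entry checks.

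The PI wording raises the same kind of problem at entry: one sentence suggests that these participants cannot change treatment, and the next changes it for all of them unless contraindicated.

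**Working it through.** No figure is involved, so the check sets the passages side by side and asks whether each ground for change can be fitted under 9.1.

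| Ground for change | Where provided for | Is it intolerance? | Result |
|---|---|---|---|
| Virologic failure or suboptimal response | 7.2 and 9.9.4 permit a change; 13.2 lists it for permanent discontinuation, then a different regimen | No, on any ordinary reading | Direct contradiction |
| Need for a prohibited medication | 13.2, with Table 1a in 9.9.2 | No | Direct contradiction |
| Creatinine clearance below 30 mL/min | 11.3 | Possibly, if the decline is drug-related; 11.3 is not limited to that case | Conflict unless intolerance is read broadly |
| Toxicity | 9.9.3, alongside intolerance | Possibly; 9.9.3 names the two separately | Conflict unless intolerance is read broadly |

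That gives two clear contradictions and two that depend on how widely intolerance is read.

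**Can the reader resolve it from 13.2?** Its cross-references were followed in turn.

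- Suboptimal virologic response is referred to Section 4.4. Section 4 ends at 4.3. Virologic failure is defined in 7.2.
- Prohibited medications are referred to Section 5.3.3. Section 5 is the hypothesis and has no subsections. The list is in 9.9.2.
- Drug-related toxicity is referred to Section 9.0 as toxicity management. Section 9 is Study Treatment, which contains the restrictive sentence. Toxicity management is Section 12.

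None of the three leads to the intended rule. Amendment Letters 1 to 3 do not alter 9.1.

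**PI users.** Four statements were compared:

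1. Transition after individual evaluation (Executive Summary).
2. Cannot receive other treatments (Executive Summary, Group C).
3. All transitioned unless a clinical contraindication exists (Executive Summary, the next sentence).
4. All Group C transitioned, with no condition (9.1).

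Statements 1 and 3 fit together, since an evaluation is how a contraindication would be found. Statement 2, as written, contradicts 3. Statement 4 omits the condition in 1 and the exception in 3.

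**The case against.** The best defence is that nothing makes 9.1 the governing sentence. Sections 9.9.3 and 9.9.4 sit in the same Section 9, are more specific, and agree with 7.2 and 13.2. The 9.1 sentence may have been meant to limit elective switching, and a sensible investigator would follow the specific sections. One might add that stopping study drug under 13.2 is not a switch. This is a fair account of what was probably intended, and it makes the problem one of drafting. It does not remove the conflict: 9.1 is not worded as a limit on elective changes, no precedence rule is stated, and 13.2 itself sends the participant to a different regimen. The treatment figure that follows the 9.1 sentence is not reproduced in the text available and might qualify it.

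The objection to the renal ground stands in part: drug-related renal decline could be called intolerance, so 11.3 is an arguable conflict only. On PI users, the sentence that they cannot receive other treatments may be background on why they were taking a PI, which makes this a secondary point.

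A reader might go further in three ways that the documents do not support.

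- **Failing participants would be left unrescued and distort the reservoir and inflammation results.** No failure rate is given and no site is told outright to withhold rescue. Section 6.1 limits reservoir modelling to ART-adherent participants. Sections 6.1 and 14.6.5 tie integration-site work to suppressed participants. A size or direction of bias cannot be derived.
- **Three active drugs must be confirmed by genotype before a PI user is moved.** Inclusion criterion 5d describes the regimen at entry, and criterion 7 concerns kidney, liver and hematologic function. Neither is a rule on resistance testing at the switch.
- **All the PI statements are mutually incompatible.** As shown above, individual evaluation and the contraindication exception are compatible.

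**Conclusion.** The contradiction is real and should be corrected. As written, 9.1 excludes two grounds for changing regimen that 7.2, 9.9.4 and 13.2 provide for: virologic failure or suboptimal response, and need for a prohibited medication. It also conflicts with 11.3 and 9.9.3 unless intolerance is given a wide meaning that the text does not state. The faulty references in 13.2 make the conflict harder to settle from the document. The PI wording is a lesser inconsistency within the Executive Summary and between it and 9.1.

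On size, the 9.1 sentence reaches every participant, because 9.1 puts all of them on this regimen: the SABES cohort, of which Section 7.1 gives 225 enrolled by March 2016 and about 250 in all, plus up to 25 new participants. The conflict bites only for those who meet one of the situations above. The protocol does not state that number, and it may be small. The conclusion rests on the ordinary meaning of only and of intolerance, and on the missing figure not changing the rule. It says nothing about which clinical rule is right.

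**What to change.** - Reconcile 9.1 with 7.2, 9.9.2 to 9.9.4, 11.3, Section 12 and 13.2, so that one consistent set of grounds for changing regimen is stated and each section refers to it.
- Correct the three cross-references in 13.2 (Sections 4.4, 5.3.3 and 9.0) so that they lead to existing, relevant sections.
- Reconcile the PI-user statements in the Executive Summary with each other and with the Group C sentence in 9.1.

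The protocol team must decide which clinical rule applies in each case; none is proposed here. The cost is one amendment letter changing wording in 9.1, 13.2, the Executive Summary and any other section the team decides to align. No visits, samples or participants are added.
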